8.2.2. Exclusion criteria

Patients meeting any of the following criteria will not be included in the study:

- Patients with prior BRAF- or MEK-inhibitor therapy
- Patients with ECOG performance status ≥ 2 (at the time of randomization for patients from COLUMBUS, during the baseline period for patients in Flatiron EHR)
- Patients with a history of leptomeningeal metastases including brain, spinal cord, or nervous system metastases (based on brain MRI or CT scan with contrast-enhanced brain MRI as the preferred assessment in COLUMBUS and based on the following

diagnostic codes in Flatiron EHR: ICD-9-CM: 198.3, 198.4 or ICD-10-CM: C79.31, C79.32, C79.40, C79.49) prior to index

For RWD patients, concurrent enrollment in a clinical trial.

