Prior systemic therapies in the adjuvant setting	Baseline Characteristic /Potential Confounder	COLUMBUS trial data; Flatiron EHR	Indicates whether patients previously received systemic therapy (e.g., prior surgery, radiotherapy, immunotherapy, or chemotherapy) before initiating treatment
Prior surgery in the adjuvant setting	Baseline Characteristic / Potential Confounder	COLUMBUS trial data; Flatiron EHR	Indicates whether patients previously used surgery to reduce/remove tumors as a form of treatment
Prior radiotherapy in the adjuvant setting	Baseline Characteristic / Potential Confounder	COLUMBUS trial data; Flatiron EHR	Indicates whether patients underwent radiotherapy among those receiving prior systemic therapy

Prior IO or chemotherapy in the adjuvant setting	Baseline Characteristic / Potential Confounder	COLUMBUS trial data; Flatiron EHR	Indicates whether patients underwent chemotherapy or immunotherapy among those receiving prior systemic therapy
Number of LOTs after TT treatment initiation	Baseline Characteristic / Potential Confounder	COLUMBUS trial data; Flatiron EHR	Indicates the number of LOTs occurring after treatment initiation $(0, 1, \ge 2$, or Missing)
Number of organs involved	Baseline Characteristic	COLUMBUS trial data; Flatiron EHR	Indicates number of organs involved or sites of metastases at baseline (1, 2, or ≥3), with all patients having at least 1 site given diagnosis of metastatic disease. This data was collected and reported in COLUMBUS. In Flatiron EHR, it will be derived based on counting the number of distinct sites recorded as having metastases based on ICD codes.
Presence of lung metastases	Baseline Characteristic	COLUMBUS trial data; Flatiron EHR	Indicates whether patients had lung metastases. This data was collected and reported in COLUMBUS. In Flatiron EHR, it will be derived based on having ICD codes reflecting presence of lung or respiratory organ metastases (ICD-9: 197, 197.1; ICD-10: C78.01, C78.02, C78.1, C78.2, C78.30, C78.39).
Presence of liver metastases	Baseline Characteristic	COLUMBUS trial data; Flatiron EHR	Indicates whether patients had liver metastases. This data was collected and reported in COLUMBUS. In Flatiron EHR, it will be derived based on having ICD codes reflecting presence of liver metastases (ICD-9: 197.7; ICD-10: C78.7)

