Presence of other metastases	Baseline Characteristic	COLUMBUS trial data; Flatiron EHR	Indicates whether patients had presence of other metastases (e.g., adrenal glands, bone, digestive tract/system, kidney, lymph nodes, reproductive organs, or unspecified sites). This data was collected and reported in COLUMBUS. In Flatiron EHR, it will be derived based on having ICD codes reflecting presence of other metastases (ICD-9: 196, 196.1, 196.2, 196.3, 196.5, 196.6, 196.8, 196.9, 197.4, 197.5, 197.6, 197.8, 198, 198.5, 198.7, 198.89; ICD-10: C77.0, C77.1, C77.2, C77.3, C77.4, C77.5, C77.8, C77.9, C78.4, C78.5, C78.6, C78.80, C78.89, C79.00, C79.01, C79.02, C79.11, C79.51, C79.52, C79.60, C79.61, C79.62, C79.70, C79.71, C79.72, C79.81, C79.89, C79.9)

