8.9. Strengths and limitations of the research methods

The strengths of this study include:

- Key inclusion criteria with respect to diagnosis, disease stage, age, BRAFV600 mutation and ECOG status in the COLUMBUS trial will be applied to the Flatiron RWD to the extent possible to obtain a comparable group of patients across both settings
- Adjustment will be made for multiple baseline characteristics to mitigate bias due to potential differences in these characteristics across the treatment groups
- Concerns about differences in outcome assessment across trial and RWD settings are
 mitigated for OS given the availability of a real-world mortality endpoint in the Flatiron
 RWD that has high sensitivity, specificity, positive predictive values, negative predictive
 values and agreement when compared against the National Death Index (NDI), the goldstandard source for mortality data in the US.¹⁷

The limitations of this study include the following:

- Application of the COLUMBUS trial inclusion criterion requiring at least 1 measurable lesion based on Response Evaluation Criteria in Solid Tumors (RECIST) version 1.1 criteria will not be implemented due to absence in Flatiron EHR of systematic radiographic imaging to assess tumor response as required by RECIST.
- While adjustment will be made for available baseline characteristics across treatment
 groups, differences due to factors that were not adjusted for may still contribute to
 observed differences in OS between settings. For instance, data on number and sites of
 metastases, while systematically collected in the COLUMBUS trial, can only be derived
 based on ICD codes in Flatiron EHR. Based on clinical input, data on number and sites
 of metastases will very likely be underestimated in the Flatiron EHR, and not
 comparable to the corresponding data from COLUMBUS, precluding adjustment for
 these variables.

- The analysis conducted here is analogous to an 'intent-to-treat' perspective, and therefore will not account for potential differences in adherence and post-baseline treatments between trial and real-world settings.
- The COLUMBUS trial was a multi-national trial that recruited patients from 160+ sites in 28 countries, and therefore covers a broader range of geographies than the US-based Flatiron RWD; differences in background care across geographies and care settings may contribute to differences in outcomes between the CTD and RWD.

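### The Flatiron ICD lists for metastatic sites are incomplete by their own pattern (C78.00, 197.2 and 197.3 are missing from lung) and give no matching rule, so the site flags will be misclassified

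*Protocol*

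**What the plan says.** Protocol 8.3 Table 1 and SAP section 5 Table 1 give the same derivations for Flatiron.

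- **Lung.** The flag rests on "having ICD codes reflecting presence of lung or respiratory organ metastases", listed as "ICD-9: 197, 197.1; ICD-10: C78.01, C78.02, C78.1, C78.2, C78.30, C78.39".
- **Liver.** One code in each system: 197.7 and C78.7.
- **Other sites.** The ICD-9 part is "ICD-9: 196, 196.1, 196.2, 196.3, 196.5, 196.6, 196.8, 196.9, 197.4, 197.5, 197.6, 197.8, 198, 198.5, 198.7, 198.89". The ICD-10 part has 28 entries, including "C79.00, C79.01, C79.02, C79.11, C79.51, C79.52, C79.60, C79.61, C79.62, C79.70, C79.71, C79.72".
- **Number of organs.** It is "derived based on counting the number of distinct sites recorded as having metastases based on ICD codes", "with all patients having at least 1 site given diagnosis of metastatic disease". The row names no code list.
- **CNS sites.** These are exclusion codes (Protocol 8.2.2): "ICD-9-CM: 198.3, 198.4 or ICD-10-CM: C79.31, C79.32, C79.40, C79.49". Their absence from the site lists is therefore not a gap.

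Protocol 8.9 says that the number and sites "of metastases will very likely be underestimated in the Flatiron EHR, and not" comparable with COLUMBUS, and that adjustment for them is ruled out. The reason given is that in Flatiron they can only be derived from ICD codes.

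**The concern.** A code list is an operational rule: whatever is not on it is recorded as absent. If the list leaves out codes that belong to the site, the flag is wrong for patients who carry only those codes, however well the EHR recorded them.

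The error is not shared equally between treatment groups. DAB+TRAM and VEM+COBI come wholly from Flatiron. ENCO+BINI pools Flatiron patients with the COLUMBUS arm (n=192), where sites were collected by the trial. A list error therefore feeds into the comparison of disease extent in Appendix Table 1.

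The same variables are candidate predictors for imputing ECOG and LDH (Protocol 8.7.3, SAP sections 6 and 7.1). Those two covariates were missing for 40-60% of the original cohort, and both enter the adjusted OS model.

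**Working it through.** No figure in the plan needs reproducing. The check sets the printed lists side by side, with the CNS exclusion codes included so that they are not counted as gaps.

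**Step 1: ICD-9 197.n against ICD-10 C78.n.**

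| Fourth character | ICD-9 listed | ICD-10 listed | Variable |
|---|---|---|---|
| 0 | bare 197 | C78.01, C78.02 | lung |
| 1 | 197.1 | C78.1 | lung |
| 2 | none | C78.2 | lung |
| 3 | none | C78.30, C78.39 | lung |
| 4 | 197.4 | C78.4 | other |
| 5 | 197.5 | C78.5 | other |
| 6 | 197.6 | C78.6 | other |
| 7 | 197.7 | C78.7 | liver |
| 8 | 197.8 | C78.80, C78.89 | other |

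Wherever both systems have an entry, the same digit goes to the same variable. The plan's own layout therefore places 197.2 and 197.3 with lung or respiratory sites, and they are the two empty cells.

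**Step 2: the zero code in C78.0x.** Six ICD-10 families are listed with both a .x1 and a .x2 code.

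- With .x0 as well: C79.0x, C79.6x, C79.7x.
- Without .x0: C78.0x, C79.3x (CNS exclusion), C79.5x.

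**Step 3: the 198 and C79 families.** C79 has entries at every fourth character except 2, and 198.2 is also absent. C79.6x is listed with no 198.6, and C79.11 with no 198.1. The documents do not say what each of these codes denotes.

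**Step 4: what bare 197 could mean.**

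| Reading | Effect on the lung flag |
|---|---|
| 197.0 with the zero dropped | 197.2 and 197.3 missed |
| Exact string 197 | 197.0, 197.2 and 197.3 missed |
| Prefix | 197.2 and 197.3 captured, but also 197.7 (liver) and 197.4, 197.5, 197.6, 197.8 (other); the listed 197.1 becomes redundant |

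The first reading fits best, since 196, 197 and 198 each stand where the zero code would be. C78.00 is missed under every reading: neither C78.01 nor C78.02 is a prefix of it.

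**Step 5: size.** Let p be the true share with lung involvement, s the share of those who carry only omitted codes, and f the share of patients without lung involvement who are wrongly captured by a prefix match.

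Observed share = p(1 - s) + (1 - p)f

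The documents give none of the three. As an illustration on assumed values only, take p = 0.40 and f = 0:

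- s = 0: 0.40 x 1.00 = 40%
- s = 0.10: 0.40 x 0.90 = 36%
- s = 0.25: 0.40 x 0.75 = 30%
- s = 0.50: 0.40 x 0.50 = 20%

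The range starts at no effect. With prefix matching f can exceed zero, and the observed share is then too high whenever (1 - p)f is larger than ps.

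**The case against.** The strongest reply is that the plan has already disclosed and contained the problem. Protocol 8.9 expects under-recording of sites in Flatiron and rules out adjustment. Table 1 does not label these rows as potential confounders, and they are in neither the listed OS adjustment set nor Appendix Table 3. Use in imputation is only to be considered, and the plan elsewhere ties the imputation models to variables eligible for adjustment. The sensitivity model with further covariates is optional. All of this stands, and it limits how far the error can travel. It does not remove the error: section 8.9 describes a limit of ICD-derived data, not codes that the plan's own list leaves out.

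A second reply is that the zero-code pattern is not universal, since C79.3x and C79.5x also lack a .x0 entry. That is fair. The pattern is strong evidence for C78.00, not proof, and the code should be verified when the list is revised. The 197.2 and 197.3 gaps do not depend on it.

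A reader might infer more than the documents support:

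- **That organ counts are understated by the plan's rule.** The count row names no code list, so the defect there is an unspecified derivation. A zero is possible only if these lists feed the count.
- **That the ICD-9 gap falls mainly on DAB+TRAM.** Its index dates start earliest, but the documents do not say when sites changed coding system.
- **That Flatiron patients are bound to look less advanced.** A prefix reading of 197 would push lung involvement upward. Flatiron ENCO+BINI patients also pass through the same lists.

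**Conclusion.** The concern holds for the site flags. The lung list is incomplete by the plan's own layout, its ICD-9 and ICD-10 parts do not correspond, and the matching rule is missing. Every reading of bare 197 leaves a defect. A patient coded only with an omitted code is recorded as not having that site, beyond the unavoidable under-recording already disclosed.

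The size is unknown and could be nil if no patient in the extract depends on an omitted code; the percentages under Step 5 of the working are illustrations, not findings. The conclusion rests on literal application of the printed lists and on the digit correspondence between 197.n and C78.n that they show.

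The point is minor. The certain effect is on the baseline tables; imputation and sensitivity models are possible routes. The primary OS hazard ratio, with its listed adjustment set, could be affected only indirectly, through imputation.

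**What to change.** In Protocol Table 1 and SAP Table 1:

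- Give one crosswalked ICD-9/ICD-10 list per site. Add C78.00, 197.2 and 197.3 to lung or respiratory sites, and add 198.2 and C79.2 to the appropriate list or justify leaving them out.
- State whether matching is exact or by prefix, and replace bare 196, 197 and 198 with the codes intended.
- Name the code-to-organ mapping used for the number of organs.
- Report a zero count in the 'Missing' row that Appendix Table 1 already has for that variable.

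The cost is a revised code list and a re-run of the derivation, with no new data. Counting the patients whose flags change would also show whether the gap matters. The non-comparability with COLUMBUS described in Protocol 8.9 would remain.

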8.4. Data sources

COLUMBUS trial

COLUMBUS was a two-part, multicenter, randomized, open-label, Phase 3 clinical trial. ¹⁰ Part 1 of the trial investigated the effectiveness and safety of three treatment regimens in patients with locally advanced unresectable or metastatic BRAFV600-mutant metastatic melanoma who were treatment naïve or whose cancer had progressed after 1L IO. In Part 1 of the trial, patients were randomized to one of three treatment arms: 1) 450mg once daily encorafenib and 45mg twice daily binimetinib (n=192), 2) 960mg twice daily vemurafenib (n=191) and 3) 300mg once daily

encorafenib (n=194). Randomization was stratified by AJCC disease stage (IIIB, IIIC, IVM1a, IVM1b, or IVM1c), ECOG performance status (0, 1), and BRAFV600 mutation profile (V600E, V600K). Progression-free survival was the primary endpoint in the trial, while OS was one of the secondary endpoints. Patients were enrolled in Part 1 of the trial between 30 December 2013 through 10 April 2015.

The ENCO+BINI arm of Part 1 of the trial will be used in this study (database lock date: 15 September 2020). Part 2 of the trial compared encorafenib 300mg once daily plus binimetinib 45mg twice daily versus encorafenib 300mg once daily alone and will not be considered.

Flatiron Health EHR

The Flatiron Health EHR database is a longitudinal, de-identified real-world database derived from EHRs collected in US cancer clinics. The database covers more than 2.6 million active cancer patients treated at over 800 sites of care across 4 US census regions. Patient-level data includes both structured (diagnosis, demographics, laboratory values, biomarker information, drug orders, visits, etc.) and unstructured (physician notes, radiology, and pathology reports, etc.) sources. Data on death is drawn from structured or unstructured data fields in the EHR, and publicly available sources of mortality including the US Social Security Death Index, and commercial obituary data. ¹³

Pfizer has contracted with Flatiron for a custom data extract containing information on patients with advanced melanoma who received treatment with BRAF- or MEK-inhibitor therapies. Patients meeting the eligibility criteria defined for this study will be obtained from this custom data extract as described in Section 8.2 and used in all analyses.

8.5. Study size

The number of patients eligible for the study will be determined in accordance with the sample selection conducted per the criteria described in Section 8.2.

8.6. Data management

Clean, patient-level datasets for COLUMBUS and Flatiron Health data will be generated for use throughout the study. This process will entail basic exploratory checks to ensure data integrity, cleaning and reformatting the raw data as needed, and creating variables for all key study measures. All data will be stored and maintained on a secure encrypted non-cloud-based server and accessed over a secure internal private wide area network. The data will be made accessible only to individuals working on the current study. No attempt will be made to identify individual patients, hospitals, or physicians. Analyses will be conducted using SAS version 9.4 and/or R version 4.1.0 or later.

8.7. Data analysis

8.7.1. Analysis of baseline characteristics

Patient baseline characteristics at or prior to the index visit will be summarized for all treatment groups. Patient characteristics to be summarized will be based on availability in both data sources and clinical input. A list of characteristics expected to be summarized is provided in Table 1.

Baseline characteristics will be summarized at the index date if measured at that time. In the Flatiron data, for baseline characteristics that are not measured at the index date, the closest available measure to the index date within a baseline period will be used. Informed by clinical input and considerations of data availability, the baseline period will be defined as a 3-month time window prior to and including the index date.

Patient baseline characteristics will be summarized descriptively using mean (with standard deviation) and median (with interquartile range) for continuous variables and count (with proportions) for categorical variables. Missingness for each baseline characteristic (at the index date or within the baseline period) will also be summarized.

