- For the real-world cohorts, patient baseline characteristics will be obtained from visits ≤3 months prior to the index date, with data from visits closest in time to the index date being used as available. In contrast, in the original protocol, to maximize availability of baseline characteristics, the 'baseline' period was allowed to include visits up to 6 months prior to treatment initiation. The decision to use a stricter definition of baseline here was based on clinical input that certain baseline characteristics of interest (e.g., ECOG PS) are best assessed closest to the index date, despite potential for increased missingness. To address missingness, imputation of baseline characteristics was conducted as described below.

- Key clinical characteristics like ECOG and LDH were missing at baseline for 40-60% of
 patients in the original study cohort, which would have hampered ability to adjust for
 potential confounding due to these factors. To address missingness, we will impute data
 using multiple imputation by chained equations prior to conducting adjusted analyses.
 Imputation models will be based on baseline characteristics that would be considered in
 adjusted models for OS.
- Inverse probability of treatment weighting without any imputation was proposed in the
 original study design to account for baseline differences. Instead, we will use
 multivariable Cox proportional hazards models fit to each of the imputed dataset and
 combined results across all imputations. This approach is preferred as it allows us to
 assess how included covariates are associated with OS in our final models, in addition to
 estimating differences between the treatments of interest.
- Comparisons of OS and PFS were stratified by first-line and second-line of therapy in the
 original study design. Analyses conducted in this revised protocol will not be stratified by
 line of therapy to allow for a larger sample size to compare OS and PFS across targeted
 therapy treatment cohorts. A line of therapy variable will be included in Cox proportional
 hazard models, which can facilitate future analyses of comparative effectiveness by line
 of therapy if required.

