8.7.3. Imputation of missing data on baseline characteristics

Previous analyses of the Flatiron data have found that there are moderate to large amounts of missing data on baseline characteristics such as ECOG performance score and LDH. ¹² As analyses restricted to patients with non-missing data are highly likely to be biased, imputation of missing data on key baseline characteristics is needed to ensure that adjusted analyses of OS between the trial and RWD settings are based on all eligible patients.

In this study, multiple imputation by chained equations (MICE)¹⁵ will be used to impute missing data on baseline characteristics. Briefly, the MICE method imputes data for a missing patient characteristic based on iterative regressions of observed data for that characteristic on observed and imputed values of other baseline characteristics. This process will be repeated for each

characteristic until stable estimates are obtained, and the entire procedure will be repeated so that multiple datasets with imputed values for baseline characteristics are created.

Baseline characteristics to be imputed will include ECOG performance score, LDH, and other clinical or demographic characteristics (e.g., race, BMI, etc.). Additional variables (e.g., age, sex, AJCC diagnosis, time from MM diagnosis to treatment initiation, time from initial diagnosis of melanoma to metastatic disease, number of organs at baseline, metastatic sites, treatments in the therapeutic setting, treatments in the adjuvant setting) will be considered for inclusion in the MICE procedure based on their relevance for adjustment and degree of missingness in the study sample. As recommended in the literature, the MICE approach will be used to create multiple datasets (e.g., 100 datasets) with imputed values, which will be used and combined in subsequent analyses. ¹⁵

Missing data on baseline characteristics will be imputed for all treatment groups. Analyses of baseline characteristics described in Section 8.7.1 will be repeated for each imputed dataset, and then summarized across all imputed datasets.

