- For the real-world cohorts, patient baseline characteristics will be obtained from visits ≤3 months prior to the index date, with data from visits closest in time to the index date being used as available. In contrast, in the original analysis plan, to maximize availability of baseline characteristics, the 'baseline' period was allowed to include visits up to 6 months prior to treatment initiation. The decision

to use a stricter definition of baseline here was based on clinical input that certain baseline characteristics of interest (e.g., ECOG PS) are best assessed closest to the index date, despite potential for increased missingness. To address missingness, imputation of baseline characteristics was conducted as described below.

- Key clinical characteristics like ECOG and LDH were missing at baseline for 40-60% of patients in the original study cohort, which would have hampered ability to adjust for potential confounding due to these factors. To address missingness, in this analysis plan we will impute data using multiple imputation by chained equations prior to conducting adjusted analyses. Imputation models will be based on baseline characteristics that would be considered in adjusted models for OS.
- Inverse probability of treatment weighting without any imputation was proposed
 in the original study design to account for baseline differences. Instead, we will
 use multivariable Cox proportional hazards models fit to each of the imputed
 dataset and combine results across all imputations. This approach is preferred as it
 allows us to assess how included covariates are associated with OS in our final
 models, in addition to estimating differences between the treatments of interest.
- Comparisons of OS and PFS will be stratified by first-line and second-line of
 therapy in the original study design. Analyses conducted in this revised analysis
 plan will not be stratified by line of therapy to allow for a larger sample size to
 compare OS and PFS across targeted therapy treatment cohorts. A line of therapy
 variable will be included in Cox proportional hazard models, which can facilitate
 future analyses of comparative effectiveness by line of therapy if required.

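### Cutting the Flatiron baseline window to 3 months leaves ECOG and LDH values from months 3–6 with no stated role in imputing the values that thereby become missing

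*Protocol*

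**What the plan says.** Protocol 8.7.1, repeated in SAP 7.1, sets the Flatiron baseline period: "the baseline period will be defined as a 3-month time window prior to and including the index date". SAP 1 records that in the original plan "the 'baseline' period was allowed to include visits up to 6 months prior to treatment initiation". Protocol 4 gives the reason for the change: on clinical advice, characteristics such as ECOG "are best assessed closest to the index date, despite potential for increased missingness". Imputation is named as the remedy.

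On the extent of the problem, SAP 1 states: "Key clinical characteristics like ECOG and LDH were missing at baseline for 40-60% of patients in the original study cohort".

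On the content of the imputation models, SAP 1 says: "Imputation models will be based on baseline characteristics that would be considered in adjusted models for OS". Protocol 8.7.3 describes the chained-equations step as "iterative regressions of observed data for that characteristic on observed and imputed values of other baseline characteristics". Further variables, given as an open list of examples, "will be considered for inclusion in the MICE procedure based on their relevance for adjustment and degree of missingness in the study sample". SAP 6 and 7.1 carry the same text. No section mentions ECOG or LDH values recorded before the 3-month window.

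**The concern.** A patient whose last ECOG or LDH was taken four or five months before the index date had a baseline value under the original window and has none now. The earlier measurement of the same quantity in the same patient is a natural predictor of the missing one, yet the plan names no use for it. Both stated selection rules also point away from it. It is not a candidate for adjustment, and it would itself be absent for many patients. A programmer following the text would have no reason to include it.

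ECOG and LDH matter here because other prognostic information is thin. Protocol 8.9 rules out adjustment for number and sites of metastases, and Protocol Table 1 says stage at treatment initiation is not available in Flatiron. All comparator patients come from Flatiron, while the ENCO+BINI group includes the COLUMBUS arm (n = 192), where ECOG was a stratification factor. The quality of imputation is therefore partly aligned with treatment group. If missingness is related to how ill the patient is, weaker imputation leaves more residual confounding in the primary hazard ratios.

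**Working it through.** The plan states no sample size, event count or missingness under the 3-month window, so there is no figure of its own to reproduce.

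**Step 1: who has an earlier value.** Let m6 be the share with no value in months 0–6, and d the extra share that becomes missing because the last value lies in months 3–6. By definition only the d group has a months 3–6 value. As a share of all missing values this is d/(m6 + d). I take m6 = 40–60% from SAP 1, reading that figure as measured under the 6-month window; d is assumed.

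| m6 | d = 5 points | d = 10 points | d = 20 points |
|---|---|---|---|
| 40% | 5/45 = 11% | 10/50 = 20% | 20/60 = 33% |
| 50% | 5/55 = 9% | 10/60 = 17% | 20/70 = 29% |
| 60% | 5/65 = 8% | 10/70 = 14% | 20/80 = 25% |

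**Step 2: how much information it adds.** With an assumed partial correlation ρ of 0.5 to 0.8 between the earlier and index values, the extra variance explained within the newly missing group is ρ² = 25% to 64%. Averaged over all missing values it is share × ρ²: from 7.7% × 0.25 = 1.9% to 33.3% × 0.64 = 21.3%.

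**Step 3: effect on the log hazard ratio.** This comes from a simulation for LDH only, with assumed inputs: 192 + 550 patients, 60% missing in Flatiron, correlation 0.7, 17% of missing values with an earlier value, 250 datasets. Error is the root mean square difference from the full-data estimate.

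- Random missingness: 0.0264 without the earlier value, 0.0251 with it.
- Missingness depending on true index LDH (log-odds 0.7): 0.0655 and 0.0620. The hazard-ratio bias factor moves from 0.944 to 0.947. On the log scale, 0.0545/0.0576 = 95% of the bias remains.

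Sampling error has to be added. With p = 192/742 = 0.259 and D deaths, SE = 1/√(D·p·(1−p)). For an assumed D of 300 this is 0.1318; for 550 it is 0.0974. Adding in quadrature, which treats the two errors as independent:

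- Random, D = 300: √(0.1318² + 0.0264²) = 0.1344 falls to 0.1342 (0.2%). D = 550: 0.1009 falls to 0.1005 (0.3%).
- LDH-dependent, D = 300: 0.1472 falls to 0.1457 (1.0%). D = 550: 0.1173 falls to 0.1154 (1.6%).

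Over shares of 17% to 33% the fall is roughly 0–3%. These figures are indicative. The same quantity without the earlier value came out at 0.0264 in one run and 0.0297 in another, 12.5% apart, and no Monte Carlo error is available.

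**Step 4: missingness that depends on the earlier value.** In an illustrative simulation with 60% missing, correlation 0.7 and 17–33% having an earlier value, bias in the log hazard ratio fell by about a quarter to a half. A second simulation was less favourable (linear outcome, n = 600, 20 imputations, 300 replicates, values missing in both treatment groups). The mean estimate moved by at most 0.003 under either mechanism, and the empirical standard error changed by between +1% (noise) and −5%. The benefit under this mechanism depends heavily on the set-up.

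**The case against.** The narrowing is deliberate, rests on clinical advice and discloses its cost. That stands: the 3-month definition is not an error, and the gap lies in the imputation specification.

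The list of additional imputation variables is open, so earlier values are not forbidden. That also stands, and a reader should not infer that the plan excludes them. But the stated basis for the models and the selection rule both steer away from them.

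A reader might infer that earlier values exist for the whole 40–60%, or for most missing values. The documents do not support this. Patients already missing under a 6-month window have nothing in months 3–6. If 60% are now missing and half of those had such a value, only 30% would have been missing under 6 months, below the stated range. Values older than 6 months might reach some of the others, but the documents do not say whether the extract holds them.

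A reader might also infer that only weak predictors such as age and BMI remain. In fact Protocol 8.7.3 lists number of organs, metastatic sites, diagnosis stage, disease timing and prior treatments as candidates, and ECOG and LDH can help predict each other.

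Finally, the auxiliary would often be absent, and no such value is described for COLUMBUS. Both are true and add to the cost.

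**Conclusion.** The point holds as a minor, inexpensive improvement. Narrowing the window turns some patients with a months 3–6 ECOG or LDH into missing cases, and the imputation text gives that value no role. It affects only the newly missing group: at most a third of missing values if 60% are now missing and at least 40% were missing under 6 months.

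Under assumed inputs the gain is about 0–3% of total error when missingness is random or depends on the true index value. It can be larger when missingness depends on the earlier value. No firm figure can be given, because neither the size of the group nor the correlation is in the documents. The result also rests on reading 40–60% as the 6-month figure, which is inferred from the amendment text, and on that range carrying over to a cohort now selected by different criteria. The material does not show that the primary comparison is seriously biased by this omission.

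**What to change.** Keep the 3-month baseline definition and the Cox model as they are. In Protocol 8.7.3 and SAP 6 and 7.1:

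- Add the most recent ECOG and LDH recorded before the 3-month window (at least months 3–6) as auxiliary predictors in the chained-equations models for Flatiron patients. State that they do not enter the Cox model.
- Run the Flatiron imputation within source, because no such value is described for COLUMBUS. Take the three Flatiron treatment groups together, since the Flatiron ENCO+BINI cohort was judged too small for adjusted analysis by itself.
- Report ECOG and LDH missingness under the 3-month and 6-month windows, by treatment group. This shows how many patients the change affects and whether the gain is material.

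The cost is some extra programming, including handling an auxiliary that is itself often missing. The values should be available because the original plan used the 6-month window, although it is an assumption that the same extract serves both analyses. If the analyses have already been run (the milestone is 7 June 2023), the imputation and adjusted models would need to be re-run.
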